1.2.3 Objectives

Primary Objective: To assess the hemodynamic effects of APD811 and the effect of APD811 on 6MWD in patients with PAH after 22 weeks of treatment including an initial dose titration period of up to 9 weeks.

Secondary Objectives: To assess the effect of APD811 on clinical worsening

Safety Objective: To assess the safety and tolerability of APD811

Exploratory Objectives:

- To assess the effect of APD811 on levels of BNP and NT proBNP after 22 weeks of treatment
- To assess change in WHO/NYHA functional class
- To evaluate the pharmacokinetics (C_{\min} and presumptive C_{\max}) of oral APD811 to evaluate the effects of APD811 on systemic vascular resistance (SVR)

1.2.4 Hypotheses

1.2.4.1 Primary Hypotheses

In patients with PAH who receive 22 weeks of treatment, APD811 compared with placebo will provide a greater reduction in PVR.

In patients with PAH who receive 22 weeks of treatment, APD811 compared with placebo will provide a greater improvement in 6MWD.

1.2.4.2 Secondary Hypothesis

In patients with PAH who receive 22 weeks of treatment, APD811 compared with placebo will provide fewer events of clinical worsening

1.2.4.3 Safety Hypothesis

In patients with PAH who receive 22 weeks of treatment, APD811 will be safe and well tolerated.

1.2.4.4 Exploratory Hypotheses

In patients with PAH who receive 22 weeks of treatment with APD811 compared with placebo will provide greater improvement on levels of BNP and NT proBNP.

In patients with PAH who receive 22 weeks of treatment with APD811 compared with placebo will provide a better improvement in SVR and/or other hemodynamic parameters.

2 DEMOGRAPHIC AND OTHER BASELINE CHARACTERISTICS

All baseline patient characteristics of demographic data (age, height, and weight), social history, medical history (abnormalities only), physical examination (abnormalities only), and concomitant medications at study entry will be listed for all patients. Demographic and baseline characteristics of the safety population will be summarized by treatment group and for the overall population. Baseline for the demographic variables will be the last pre-randomization value. Continuous variables will be summarized using number of observations (n), mean, standard deviation (SD), median, minimum, and maximum. Frequencies and percentages will be reported for all categorical data. No formal statistical testing comparing treatment groups will be performed.

The following variables will be summarized by treatment group:

1. Continuous baseline demographic variables: age (years) - the years between the date of informed consent and the date of birth
2. Categorical baseline demographic variables: sex (female or male), ethnicity (Hispanic/Latino or Not Hispanic/Not Latino) and race (American Indian or Alaska Native, Asian, Black or African-American, Native Hawaiian or Other Pacific Islander, White or Caucasian, or Other).
3. Pulmonary Arterial Hypertension history include:
 - Duration of PAH (in years): the years between the date of PAH diagnosis and the date of randomization, the incomplete date will be calculated by year.
 - PAH Classification (Idiopathic PAH, Heritable PAH, Drugs or toxin induced, Associated PAH)
 - PAH Disease Specific Concomitant Medication by category
 - With ERA vs. without ERA
 - With PDE5 vs. without PDE5
 - With sGC vs. without sGC
 - Monotherapy ERA
 - Monotherapy PDE5
 - Monotherapy sGC
 - Combination therapy ERA + PDE5
 - Combination therapy ERA + sGC
 - Baseline WHO/NYHA Function Classification
 - Baseline PVR
 - Baseline 6-Minute Walk Test
 - Baseline BNP/NT-proBNP

3 PATIENT DISPOSITION

The number of patients enrolled in the study by investigator and treatment group will be tabulated. Tables showing study participant accounting will be provided. Tables will indicate number of patients who were randomized into the study, the number of patients who completed the study, and the number of patients who discontinued prematurely (early termination) for any of the following reasons:

- Clinical worsening
- Deviation/noncompliance with the protocol or study drug
- Adverse event(s)
- Investigator decision
- Sponsor decision
- Patient withdrawal of consent
- Patient lost to follow up
- Death
- Other

4 EFFICACY ANALYSES

4.1 Efficacy Endpoints

A table is provided in Appendix 3 summarizing the efficacy variables and their analysis populations.

Primary Endpoints

The primary endpoints are listed below:

- Change from baseline in PVR after 22 weeks of treatment
- Change from baseline in 6 MWD after 22 weeks of treatment.

Secondary Endpoints

Secondary efficacy variables include:

- Percent change from baseline in PVR after 22 weeks of treatment
- Proportion of patients who progress to clinical worsening

Exploratory Endpoints

The exploratory efficacy endpoints are listed below:

- Change from baseline in BNP and NT-proBNP after 22 weeks of treatment
- Change from baseline in SVR and other hemodynamic parameters (listed in Section 1.2.2.3) after 22 weeks of treatment
- Change from baseline in WHO/NYHA functional class in numeric scale after 22 weeks of treatment
- Proportion of patients in categorical change of WHO/NYHA function class after 22 weeks of treatment. Three ordinal categories are defined as Improved, No Change, and Deteriorated, in comparison with baseline
- Longitudinal change from baseline in 6 MWD up to 22 weeks
- Longitudinal change from baseline in WHO/NYHA functional class in numeric scale up to 22 weeks
- Time to first event of clinical worsening, the duration is defined as from randomization to first occurrence of clinical worsening, otherwise it will be censored at the last record date of clinical worsening event assessment or end of study, whichever is latest.

4.2 Analysis Population

The primary analysis of the efficacy endpoint, PVR, will be conducted using the intent to treat population.

Intent-to-Treat Population (ITT):

This population consists of all patients randomized who receive at least one dose of study drug, and have a baseline PVR measurement. Under this approach, patients are counted in the treatment group to which they were randomized, regardless of the treatment received during the course of the trial. The primary endpoint, PVR change from baseline at Week 22, will use this population for analysis.

Unless otherwise specified, the analyses of all other efficacy variables will use the modified intent to treat (MITT) population as primary. The completers population will be used as a secondary analysis population.

Modified Intent-to-Treat Population (MITT):

This population consists of all patients randomized who received at least one study dose, have a baseline measurement, and have a post-randomization measurement. Under this approach, patients are counted in the treatment group to which they were randomized, regardless of the treatment received during the course of the trial.

Completers Population (CP):

This population consists of all patients who completed the study treatment at Week 22. No missing data will be imputed for this analysis. Any substantial differences between conclusions based on the ITT, MITT and the completers' populations will be investigated.

Safety Population (SP):

The Safety Population will include all randomized patients who received at least one dose of study medication.

4.3 Approaches to Efficacy Analysis

4.3.1 Primary Efficacy Analysis

The primary efficacy hypothesis regarding the superiority of APD811 to placebo will be assessed in a stepwise manner. First, the statistical significance of APD811 versus placebo result will be determined for the change from baseline in PVR at the end of 22 weeks of treatment. If the result is significant ($p < 0.05$, two-sided), the primary hypothesis will be considered satisfied and this study will be declared positive. Subsequently, the change from baseline in 6MWD will only be formally tested if the change from baseline in PVR is significant. This testing procedure preserves the overall Type I error rate for testing the primary efficacy hypothesis.

In this first-in-patient Phase 2 study in PAH patients, there is a clinical rationale to specify two important primary endpoints: the key hemodynamic parameter, PVR; exercise capacity as measured by 6MWD. Right heart catheterization from which PVR is derived only takes place at Screening and Week 22; 6MWD is measured at Screening, baseline, and at 5 post-baseline specified time points.

In cases of missing data occurring at Week 22, the following missing data handling rules will apply.

For PVR, assessments measured at Week 22 or at time of early withdrawal will be included in the analysis. Missing data at Week 22 will be imputed using the method of multiple imputation as outlined in Section 7.4 and detailed in Appendix 4. For 6MWD, missing values will be imputed with the last observation carried forward (LOCF), except if any patient withdraws early due to death or due to clinical worsening without a 6MWT being measured at a termination visit, a worst value of 0 for 6MWD will be imputed. Baseline assessments will not be carried forward.

To further assess missing data impacts on primary analyses, the completers analyses without data imputation will be performed and compared with additional sensitivity analyses specified in Section 7.4.

An analysis of covariance (ANCOVA) model with baseline PVR as a covariate and treatment and baseline WHO/NYHA functional class (II vs, III or IV) and baseline background PAH therapy (With ERA vs. Without ERA) as factors will be used to assess the effect of APD811 on change from baseline in PVR. LSM means for the treatments and the treatment effect and LS Mean difference between treatment will be displayed with 95% CIs and the two-sided p-value will be displayed. The normality of the model residuals will be assessed using Shapiro-Wilks test. Assumptions for the analysis of covariance will be checked, and if not satisfied, parametric analyses will be corroborated with appropriate nonparametric analyses, such as the Wilcoxon rank sum test stratified by baseline WHO/NYHA functional class (II vs, III or IV) and baseline background PAH therapy (With ERA vs. Without ERA). The Hodges-Lehmann estimation of location shift and confidence interval will be produced. If the model residuals is not normally distributed, ANCOVA analysis based on log-transformed data will be performed.

Six minute walking distance (6MWD) will be analyzed using the above ANCOVA method described for PVR, substituting the 6MWD baseline measurement as the covariate. Assumptions for the analysis of covariance will be checked, and if not satisfied, parametric analyses will be corroborated with nonparametric analyses, such as the Wilcoxon rank sum test stratified by baseline WHO/NYHA functional class (II vs, III or IV) and baseline background PAH therapy (With ERA vs. Without ERA). The Hodges-Lehmann estimation of location shift and confidence interval will be produced.

Note that formal testing for secondary and exploratory endpoints will proceed only if the comparison for the change from baseline in PVR is significant. In the event that the treatment effect for PVR is non-significant all subsequent testing of other endpoints will be interpreted only in an exploratory, rather than confirmatory manner.

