# 9.5.2 Statistical Analyses of Efficacy Measurements

## 9.5.2.1 Primary Efficacy Analysis

The primary endpoints are listed below:

- Change from baseline in PVR after 22 weeks of treatment
- Change from baseline in 6 MWD after 22 weeks of treatment.

The primary efficacy hypothesis regarding the superiority of APD811 to placebo will be assessed in a stepwise manner. First, the statistical significance of APD811 versus placebo result will be determined for the change from baseline in PVR at the end of 22 weeks of treatment. If the result is significant (p < 0.05, two-sided), the primary hypothesis will be considered satisfied and this study will be declared positive. Subsequently, the change from baseline in 6MWD will only be tested if the change from baseline in PVR is significant. This testing procedure preserves the overall Type I error rate for testing the primary efficacy hypothesis.

An analysis of covariance (ANCOVA) model with baseline PVR as a covariate and treatment and baseline WHO/NYHA functional class as factors will be used to assess the effect of APD811 on change from baseline in PVR. Missing values will be imputed using the last observation carried forward (LOCF) method. Assumptions for the analysis of covariance will be checked, and if not satisfied, parametric analyses will be corroborated with nonparametric analyses or with appropriate data transformations if necessary (i.e., log transformation).

Six minute walking distance (6MWD) will be analyzed using the above ANCOVA method described for PVR, substituting the relevant baseline measurement as the covariate. Missing values will be imputed with last observation carried forward, except if any patient withdraws early due to death or due to clinical worsening without a 6MWT being measured at a termination visit, a worst value of 0 for 6MWD will be imputed.

Note that testing for secondary and exploratory endpoints will proceed only if the comparison for the change from baseline in PVR is significant.

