1.2 Description of the Study and Objectives/Hypotheses

1.2.1 Summary of Study Design

APD811-003 is a 22 week, randomized, double-blind, placebo controlled study which includes a dose titration period of up to 9 weeks. An additional transition period of 3 weeks (± 1 week) will occur for those patients who elect to enroll into the open-label extension study, APD811 007. Patients that do not continue in the extension study will have a 3 week follow-up visit. Patients will be randomized 2:1 active to placebo. Approximately 60 patients with PAH will be enrolled. At the end of the treatment period, all patients that choose to continue in the open-label extension study (OLE: APD811-007) will remain on study treatment until the follow-up visit at Week 25. This visit will serve as the baseline visit for the open-label extension study if the patient is eligible and chooses to participate (see Appendix 1). Patients who do not choose to participate in the OLE will discontinue treatment at the end of the treatment period.

Safety will be assessed by the Safety Monitoring Committee (SMC) as documented in the SMC Charter. The SMC will review safety data including adverse events, blood pressure and heart rate periodically during the dose titration period and the treatment period, in order to ensure patient safety and determine an appropriate dose titration regimen.

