7 STATISTICAL TECHNICAL ISSUES

7.1 Planned Statistical Power and Sample Size

For the APD811 versus placebo comparison, 28 patients in the APD811 group and 14 patients in the placebo group will have 90% power to detect a between-treatment difference of 350 dyn·s·cm⁻⁵ in PVR. This calculation was based upon the pooled SD estimate of 320.3 dyn·s·cm⁻⁵ for the mean change from baseline in PVR at Week 17 observed in the selexipag phase 2 study.

Assuming that up to 30% of patients may drop out of the trial before a post-randomization repeat RHC is performed, 40 patients will be randomized to the APD811 group and 20 patients will be randomized to the placebo group. For 6MWD, 40 patients in APD811 group and 20 patients in the placebo group will have 80% power to detect a between-treatment difference of 50 meters in 6MWD assuming pooled SD estimate of 65 meters.

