7.4 Handling of Missing Data and Sensitivity Analysis

For the ITT analysis of PVR missing week 22 assessments will be derived using the method of multiple imputation via the SAS/STAT procedure PROC MI and the fully conditional

specification (FCS) method to create 100 imputations resulting in 100 complete datasets. The 100 imputed datasets will then be analyzed using the methods described in Section 4.3.1, with the results of the analyses performed on the 100 datasets combined via PROC MIANALYZE. The imputation model will include the following variables: treatment, baseline PVR, baseline NYHA/WHO functional class category, baseline PAH therapy, baseline values for 6MWD, BNP, NT-proBNP, etiology, last on-treatment 6MWD and whether or not a patient experienced clinical worsening. It is anticipated that the imputation model will converge but should it not do so terms will be removed from the model to achieve convergence. The effects of any such model adjustment will be investigated.

To assess the impact of missing data and robustness of the results, the following sensitivity analyses will be performed for the primary, secondary and selected exploratory endpoints:

- Completers population analyses on primary and secondary efficacy endpoints will be performed without missing data imputation.
- Worst case imputation. For PVR, in all-treated patients, prior to ANCOVA analyses as detailed in Section 4.3.1 missing data at Week 22 due to any reason will be imputed by taking:
 - the worst percentage change from baseline in all patients regardless of treatment group.
 - the baseline observation carried forward.
- An additional 'tipping point analysis' *may* be performed for PVR, post-hoc, in the event that the primary analysis is statistically significant and at least 1 of the worst case imputation analyses yields a non-significant result.

For the proportion of patients who progress to clinical worsening, a sensitivity analysis to assess the impact of missing data will be performed wherein all patients who prematurely discontinue treatment for any reason will be considered to have had a clinical worsening event.

- Imputation of missing or incomplete AE start date
 - If year part of AE start date is missing, then the year of the first treatment date will be assigned.
 - If both month and day part of AE start date are missing, and the year part is the same as year of the first treatment date, then the first treatment date will be assigned;

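### The nonparametric back-up named for PVR and 6MWD omits the baseline value and splits a small sample into four strata; rank ANCOVA would be a stronger supportive test, chiefly for 6MWD

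*SAP*

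**What the plan says.** - **Primary model (SAP 4.3.1).** Change in PVR is analysed by ANCOVA with baseline PVR as covariate and treatment, functional class (II against III or IV) and background therapy (with or without ERA) as factors. 6MWD uses the same model, "substituting the 6MWD baseline measurement as the covariate".
- **Back-up (SAP 4.3.1).** If assumptions fail, "parametric analyses will be corroborated with appropriate nonparametric analyses, such as the Wilcoxon rank sum test stratified by baseline WHO/NYHA functional class"; the sentence goes on to add ERA use as a second stratifier. The 6MWD paragraph names the same test. For both endpoints, "The Hodges-Lehmann estimation of location shift and confidence interval will be produced".
- **Log scale.** For PVR, 4.3.1 adds an ANCOVA on log-transformed data if residuals are non-normal, and 4.3.2 analyses the log ratio of Week 22 to baseline in any case. The 6MWD paragraph of 4.3.1 has no such step; only the SAP synopsis mentions transformation in general terms.
- **Missing data.** For 6MWD, 4.3.1 imputes 0 m after death or clinical worsening without a termination walk. For PVR, 7.4 creates 100 imputed datasets and analyses them by the methods of 4.3.1, "with the results of the analyses performed on the 100 datasets combined via PROC MIANALYZE". Appendix 4 programs only the linear model and a count of imputations with non-normal residuals.

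**The concern.** A change score subtracts baseline but does not adjust for it. If patients with a higher baseline PVR tend to fall further, or those with a short baseline walk tend to gain more, ANCOVA removes that variation and a rank test on the raw change leaves it in. Baseline is measured in every analysed patient, so nothing prevents a rank-based analysis from using it.

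The stratification adds a second cost. With 42 patients in four strata the average stratum holds 42/4 = 10.5; with 60 it holds 15. If functional class splits 50/50 and ERA use 70/30 (both assumed), the smallest strata have 14 × 0.5 × 0.3 = 2.1 placebo patients for PVR and 20 × 0.5 × 0.3 = 3 for 6MWD.

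What is at stake is the reading of the supportive evidence. A back-up may fail to agree with the ANCOVA merely because it is a weaker test than one that could have been run on the same data.

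**Working it through.** **1. Inputs.** From the documents: the 0.05 two-sided level (Protocol 9.5.2.1, "If the result is significant (p < 0.05, two-sided"); allocation (SAP 1.2.1, "Patients will be randomized 2:1 active to placebo"); PVR difference 350 (SAP 7.1, "28 patients in the APD811 group and 14 patients in the placebo group will have 90% power to detect a between-treatment difference") with its SD ("This calculation was based upon the pooled SD estimate of 320.3"); 6MWD difference 50 m, SD 65 m, 40 + 20 patients (SAP 7.1). Assumed, because the documents do not state them: the correlation ρ between baseline and change, the error shape, the split of functional class and ERA use, and the rate of 0 m imputations.

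**2. The plan's own power.** Normal approximation: power = Φ(δ / [σ√(1/n₁ + 1/n₂)] − 1.96).
- PVR: σ√(1/28 + 1/14) = 104.8; 350/104.8 = 3.34; power 91.6% (noncentral t: 90.3%). Stated: 90%.
- 6MWD: 65√(1/40 + 1/20) = 17.8; 50/17.8 = 2.81; power 80.2% (noncentral t: 78.9%). Stated: 80%.

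Both reproduce. Neither involves ρ.

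**3. Stratified Wilcoxon against rank ANCOVA.** The Wilcoxon is the van Elteren test on four strata. Rank ANCOVA regresses the rank of change on treatment, rank of baseline, functional class and ERA. There were 2,000 simulated trials per cell (error about 1 point), with functional class correlated 0.4 with baseline and ERA use 70%.

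| Setting | ρ = 0 | ρ = −0.3 | ρ = −0.5 |
|---|---|---|---|
| 6MWD 40/20, normal errors | 72 v 74% | 74 v 78% | 74 v 86% |
| 6MWD 40/20, 0 m in 5% active and 10% placebo | 70 v 73% | 69 v 74% | 71 v 81% |
| PVR 28/14, normal errors, effect 350 | 83 v 85% | 84 v 89% | 83 v 94% |
| PVR 28/14, t₃ errors, effect 250 | 81 v 84% | 76 v 84% | 73 v 89% |

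Other runs place the gain at about 2–4, 3–8 and 8–18 points at the three correlations. A repeat of the 0 m case gave 70 v 73, 72 v 75 and 71 v 79%. Heavy-tailed PVR with effect 250 gave 69 v 87% at −0.5 and, just outside the range, 75 v 85% at −0.3. Where power is already above 90% the gain shrinks: PVR with t₃ errors and effect 350 gave 95.5 v 96.9, 95.3 v 97.8 and 93.5 v 98.4%. Type I error was 4.5–5.7% (Wilcoxon) and 4.4–5.8% (rank ANCOVA).

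**4. How much is due to baseline.** Splitting the change into two steps at ρ = −0.3, normal errors:
- PVR: stratified Wilcoxon 82.9%; rank regression on treatment, class and ERA without baseline 87.6%; with baseline 89.2%. So 4.7 of 6.3 points come from dropping the strata.
- 6MWD: 71.6, 75.5 and 78.6%. So 3.9 of 7.0 points come from dropping the strata.

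At ρ = 0 the baseline term costs a little (6MWD 75.9 to 75.1%, PVR 86.2 to 85.6%). If the strata are kept and baseline ranks are added within them, 6MWD with normal errors goes from 71.2 to 70.6% at 0, 73.3 to 74.9% at −0.3 and 73.7 to 81.0% at −0.5.

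**5. Against the parametric ANCOVA.**
- 6MWD with 0 m in 5% and 10%, ρ = 0, −0.3, −0.5: Wilcoxon 72, 71, 70%; ANCOVA 53, 53, 53%. Shapiro-Wilk gave p < 0.05 in 97–98% of these trials.
- PVR, t₃ errors, effect 250: Wilcoxon 82 v ANCOVA 70% at 0, 77 v 73% at −0.3, 71 v 79% at −0.5.
- PVR with a multiplicative effect and skewed baseline: ANCOVA 75–92%, Wilcoxon 68–84%, rank ANCOVA 78–92%, log-ANCOVA 83–95%.

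The PVR runs used complete 28/14 data and did not simulate the multiple imputation.

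**The case against.** - **The Wilcoxon does its job.** A reader might infer that the back-up loses power in the very situation it is meant to protect. Step 5 does not support that: with 0 m imputation at those rates it beats the failing ANCOVA by a wide margin, and with heavy-tailed PVR it does so at low correlation. It trails for heavy-tailed PVR at −0.5 and for multiplicative PVR effects, and is about level for 6MWD if zeros are assumed in 2.5% active and 15% placebo (ρ = 0: 82.6 v 83.0%). The loss is relative to rank ANCOVA only.
- **The missing baseline is not the whole cause.** This stands. At −0.3 more than half of the gain in step 4 comes from replacing the strata, and baseline matters materially only near −0.5 or beyond. The documents do not show where the true correlation lies.
- **PVR is already covered.** This largely stands. The planned log-ANCOVA keeps baseline and did better than rank ANCOVA in the multiplicative scenario. It does not help 6MWD, where a log cannot be taken of an imputed 0 m.
- **The SAP gives the Wilcoxon only as an example.** True, so rank ANCOVA is allowed. But the choice then remains open after the data are seen.
- **Pooling is not peculiar to rank ANCOVA.** Fair. A Hodges-Lehmann estimate with a standard error could also be combined. The gap is that no rule is stated for any rank analysis over the 100 datasets.
- **No decision depends on it.** A reader might infer that the trial's conclusion is at risk. Nothing in 4.3.1 lets the back-up replace the ANCOVA p-value in the stepwise test.

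**Conclusion.** The point holds as a modest improvement to a supportive analysis. The named test omits the baseline value and uses four thin strata. Rank ANCOVA on the same data kept the type I error near 5% and had higher power at each correlation examined, by the amounts in step 3. Those amounts rest on assumed correlations, error shapes and stratum splits, and they combine two changes, of which baseline adjustment is one.

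The case is strongest for 6MWD: the 0 m rule makes non-normal residuals likely, and the rank test is then the only back-up that 4.3.1 names. For PVR the gain is secondary to the log-ANCOVA already planned, although a pooling rule for the rank analysis is still missing.

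**What to change.** In SAP 4.3.1:
- For 6MWD, pre-specify rank ANCOVA (rank of change on treatment, rank of baseline, functional class and ERA use) as the nonparametric analysis.
- For PVR, pre-specify the same analysis alongside the log-ANCOVA. Fit it in each of the 100 imputed datasets and pool the treatment coefficient and its standard error with PROC MIANALYZE; add this to Appendix 4.
- Keep the Hodges-Lehmann shift and interval as planned for the size of effect, and state how it is combined over the imputed PVR datasets.
- Keep the stratified Wilcoxon as a secondary check.

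The cost is a few lines of SAS and SAP text, with no new data. The drawback is that a rank coefficient is not in metres or dyn·s·cm⁻⁵, which is why the Hodges-Lehmann estimate must stay.
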